Contact IRT	X	X	Х	X	X	X	X	Х	X	X	Х		
Dispense study medication	X	X	X	Х	X	X	X	Х	X	X			
Collect study medication	X	X	X	Х	X	X	X	Х	X	X	х		
PASI, sPGA	X	X	X	X	X	X	X	X	X	X	X		
Columbia-Suicide Severity Rating Scale (C-SSRS) ⁷	X	x	x	x	x	x	x	x	x	x	x	X	
Safety laboratory samples	X	X	Х	X	X	X	X	X	X	X	X		
Biomarker samples (serum)											Х		
Whole blood (PBMC)													
for flow cytometry											X		
(pre-dose) ⁸													

Page 8 of 84

Trial Periods		Open Label Treatment										Follow-Up
Visit	15	16	17	18	19	20	21	22	23	24	EOT^{12}	\mathbf{EOO}^{11}
Week	168	180	192	204	216	228	240	252	264	276	288	292
Visit window (days)	±7	±7	±7	±7	±7	±7	±7	±7	±7	±7	±7	+7
Termination of trial medication											X	
Trial completion ^{10, 11}												X
Vital status collection ¹³												X

Boehringer Ingelheim 06 Oct 2020

Clinical Trial Protocol Page 9 of 84

Proprietary confidential information © 2020 Boehringer Ingelheim International GmbH or one or more of its affiliated companies

Flow Chart Footnotes:

Visit 1 will occur on the same day as End of Treatment (EOT) Visit in 1407-0030. Weight, vital signs, physical exam, ECG, pregnancy test, PASI, sPGA,

, C-SSRS, biomarker samples, whole blood

(PBMC) for flow cytometry and are performed only once on that day as part of the EOT Visit in 1407-0030. Visit 1 may be delayed up to 16 weeks if necessary for administrative reasons. If Visit 1 is delayed, these procedures will be done at Visit 1, except for PK, Biomarker and flow cytometry samples.

² Safety laboratory samples will be taken twice in the same day as part of both the EOT Visit in 1407-0030 and for Visit 1 in 1407-0005. Visit 1 collection is only for the following laboratory tests that are not assessed at EOT in study 1407-0030: infection testing, glycosylated Hbc, LDL-cholesterol/HDL-cholesterol, cholesterol total, and triglycerides. If Visit 1 is delayed, then a sample will be taken at Visit 1 to include all tests included in the two samples and only one sample will be taken at EOT for 1407-0030.

³For patients entering from Part 1 of trial 1407-0030, Visit 2.1 is a phone visit, with only adverse events and concomitant medication collected. Visits 1.1, 1.2 and 1.3 do not apply. For patients entering from Part 2 of trial 1407-0030, Visits 1.1, 1.2 and 1.3 to be performed at the clinic with all procedures indicated, Visit 2.1 does not apply.

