All patients entering the extension trial are to be assigned at Visit 1 to receive openlabel treatment with 400 mg q.d. (fed), the anticipated therapeutic BI 730357 dose. Refer to Figure 3.1: 2.

It is expected that Visit 1 of trial 1407-0005 will be performed on the same day of the EOT Visit of trial 1407-0030 in both patient groups. In the event that patients completing Part 2 of trial 1407-0030 are not able to be entered immediately into the extension trial due to administrative reasons (e.g., pending protocol approval, availability of trial medication), Visit 1 of the extension trial may be delayed for no more than 16 weeks. In the event of a delay, the CTM should be consulted and refer to the Flow Chart for procedures to be conducted.

The treatment period is this trial will be approximately 6 years.

[figure not shown]

Figure 3.1: 1 Trial 1407-0005 dose assignment/reassignment for patients entering from Part 1 of trial 1407-0030

[figure not shown]

Figure 3.1: 2 Trial 1407-0005 dose assignment for patients entering from Part 2 and continuing from Part 1 of trial 1407-0030

Page 28 of 84

Clinical Trial Protocol

Dose selection at Week 12 is based on the safety and tolerability data from the SRD Trial 1407.1 and the MRD Trial 1407-0002, and will be contingent on DMC evaluation of all available data from Phase II trial 1407-0030. For patients entering from Part 1 of trial 1407-0030, if an unacceptable risk regarding the safety of the 200 mg dose level is reported by the DMC, the open label BI 730357 dose assignments beginning at Week 12, as shown in Figure 3.1: 1, is to be altered to assign all patients to the 100 mg *q.d.* dose group. For additional

details and logistics, refer to Section 8.7. Refer to Section 4.1.2 for dose selection rationale.

All patients entering from Part 2 of trial 1407-0030 are to receive the 400 mg q.d. dose, as long as no unacceptable risks are identified during Part 2 of trial 1407-0030. Once Part 2 patients begin enrolling in this trial, existing patients receiving 100 mg q.d. in this trial will be given the option to titrate up to the 200 mg q.d. dose, if the investigator determines that the patients may benefit from the higher dose.

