6.2.2 Treatment period

The treatment period starts with Visit 1 and ends with the EOT visit. The patients will be fasted for each visit.

The patients will return to the clinic for regularly scheduled visits as specified in the Flow Chart. At these visits, the occurrence of safety and efficacy endpoints, trial medication compliance, concomitant therapy or intervention will be assessed.

At all treatment visits, the order of assessments (as applicable) should be followed:

- Completion of the questionnaires
- Physical examination, urine pregnancy, vital signs, and ECG
- Laboratory samples

All assessments must be performed before the medication is taken.

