6. GENERAL ANALYSIS DEFINITIONS

6.1 TREATMENT(S)

All patients need to complete the preceding Phase II psoriasis Trial 1407-0030 and meet entry criteria for this study.

Two groups of patients are to be entered into this trial, including up to (approximately) 180 patients entered in the original trial 1407-0030 protocol (now Part 1) and approximately 90 patients entered in an extended dose-ranging segment, now Part 2 of the amended trial 1407-0030 protocol. Actual numbers of subjects entering the extension trial are to be determined by response in the preceding study.

In the first group (Part 1), patients will be considered eligible to participate in this long-term extension trial upon completing the trial 1407-0030 Week 24 end-of-treatment visit with a \geq PASI50 response. BI 730357 dose levels of up to 200 mg *q.d.* are to be administered under fasting conditions to patients in this group, reflecting the dose levels evaluated during Part 1 of trial 1407-0030.

- Patients entering the extension trial will remain on their blinded BI 730357 dose treatment from the preceding trial until the open label period of 1407-0005 begins at Visit 2/Week 12.
- At Visit 2/Week 12, patients presently assigned to double blind treatment of placebo, 25 mg, 50 mg, and 100 mg will be reassigned to the 100 mg open label dose, and patients presently assigned to the double blind treatment of 200 mg will be reassigned to 200 mg open label dose.

In the second patient group (Part 2), patients will be considered eligible to participate in this trial upon completing the trial 1407-0030 Week 12 end-of-treatment visit with a \geq PASI50 response or perceived patient improvement, at the discretion of the Investigator. Patients are to be considered eligible only if also without ongoing AEs consistent with intolerance of trial medication (including gastric intolerance) that in the opinion of the investigator would compromise the safety of the patient.

.

- All patients entering the extension trial are to be assigned at Visit 1 to receive open-label treatment with 400 mg *q.d.* (fed), the anticipated therapeutic BI 730357 dose.

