7.8.2 Laboratory data

The analyses of laboratory data will be descriptive in nature and will be based on BI standards [\(6\)](#). The number and percent of patients with possibly clinically significant on treatment abnormalities as identified by use of clinically significant ranges for each laboratory parameter collected will be presented. The patients from both parts of 1407-0030 with possibly clinically significant abnormalities will be identified by actual treatment received at study entry.

Each laboratory value will be graded using the RCTC (version 2.0) grading of laboratory abnormalities. A summary table of the baseline grade compared with the last available on treatment grade will display the number and percent of each type of transition in grade by laboratory parameter within each treatment period and treatment group. A second table will show the number and percent of patients with each type of transition from baseline to their worst on-treatment grade.

A graphical summary highlighting potential cases of Hy's Law by actual treatment received at study entry will be presented. The maximum on-treatment values of total bilirubin and ALT will be plotted each on a scale as multiples of the upper limit of normal. The figure will show areas that meet the criteria of cholestasis (total bilirubin $> 2 \times$ ULN), Temple's corollary (ALT $> 3 \times$ ULN) and Hy's Law as the combination of these two factors. A similar figure using maximum AST values in place of ALT will be constructed. An accompanying listing will show by sample date and study day the full course of the total bilirubin, ALT, AST and alkaline phosphatase values for patients whose total bilirubin are $> 2 \times$ ULN or AST or ALT values $> 3 \times$ ULN at any time during the study (all treatment periods). The listing will indicate where the value meets the criteria, either falling in the cholestasis range, that for Temple's corollary or where the combination meets that for Hy's Law itself.

Laboratory measurements taken up to the residual effect period of 7 days after the last administration of study drug will be considered as on-treatment.

Study visits will be presented by the Visit labels in [Table 6.7:1](#).

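### SAP 7.8.2 labels whole-study laboratory abnormality counts and Hy's Law figures by entry dose, which 25 mg and 50 mg entrants leave at Week 12 and 100 mg patients may leave later

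*SAP*

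**What the plan says.** SAP 7.8.2 plans a count of patients with possibly clinically significant on-treatment abnormalities and states that "patients from both parts of 1407-0030 with possibly clinically significant abnormalities will be identified by actual treatment received at study entry". It then plans a figure of potential cases of Hy's "Law by actual treatment received at study entry will be presented". For that figure, "The maximum on-treatment values of total bilirubin and ALT will be plotted", and a similar figure uses AST. No period split is stated for either figure. Under SAP Table 6.1: 1, on-treatment runs from the first dose to the last dose plus the 7-day residual effect period, so it spans every dose change.

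The doses do change. At Week 12, Part 1 patients on "placebo, 25 mg, 50 mg, and 100 mg will be reassigned to the 100 mg open label dose" (SAP 6.1). Under Protocol 3.1, once Part 2 patients begin enrolling, "existing patients receiving 100 mg q.d. in this trial will be given the option to titrate up to the 200 mg q.d. dose".

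Other parts of the SAP bear on the label:

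- SAP 6.3 bases the Treated Set on the actual treatment received at enrolment.
- SAP 6.1 plans laboratory summaries for the entire study, the first 12 weeks and after 12 weeks.
- In SAP 7.8.2, the baseline-to-last-grade table is "by laboratory parameter within each treatment period and treatment group", and the liver listing shows sample dates and study days.

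**The concern.** The label names the dose at entry, while the value displayed can come from any later time on treatment. For a 25 mg or 50 mg entrant who stays in the trial, nearly all later values arise on 100 mg, or on 200 mg after titration. An ALT peak on 100 mg would be plotted as a 25 mg point, and an abnormality first seen on 200 mg could be counted under 50 mg.

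Long-term safety is the trial's purpose, and drug-induced liver injury is a named concern in Protocol 1.4. Protocol 7.3.4 intends treatment groups to be compared descriptively on the frequency of abnormal values, so the column label carries the message of the display. The laboratory displays would also not line up with the adverse event tables by dose at onset in the same report.

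**Working it through.** The plan gives no figure on this point, so there is none to reproduce. The check counts scheduled samples by the dose being taken.

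**Inputs**

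- Protocol Flow Chart, safety laboratory row: for a Part 1 entrant, on-treatment samples fall at Visit 2 (Week 12), Visits 3 to 14, Visits 15 to 24 and EOT (Week 288). The Visit 1 sample precedes the first dose in this trial and is not counted.
- Flow Chart footnote 3, for Part 1 entrants: "Visit 2.1 is a phone visit, with only adverse events and concomitant medication collected. Visits 1.1, 1.2 and 1.3 do not apply". There is thus no scheduled sample between Day 1 and Week 12.
- Protocol 6.2.2: "All assessments must be performed before the medication is taken". The Week 12 sample therefore belongs to the entry dose.
- Protocol synopsis ranges: 25 mg 0 to 40 patients, 50 mg 0 to 80, placebo 0 to 20, open-label 100 mg 80 to 140.

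**Samples on and off the labelled dose**

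Total to Week 288: 1 + 12 + 10 + 1 = 24. On the entry dose: Visit 2 only = 1. Share off the labelled dose = (N − 1)/N.

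| Followed to | Visits | N | On entry dose | On a later dose | Share off label |
|---|---|---|---|---|---|
| Week 48 | 2–5 | 4 | 1 | 3 | 75.0% |
| Week 96 | 2–9 | 8 | 1 | 7 | 87.5% |
| Week 288 | 2–24, EOT | 24 | 1 | 23 | 95.8% |

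In planned time to Week 288, the entry dose covers 84 of 2016 days: 84/2016 = 4.2%.

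**Patients affected**

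25 mg and 50 mg entrants: minimum 0, maximum 40 + 80 = 120. The maximum is an extreme: the open-label 100 mg ceiling of 140 also includes 100 mg entrants, and 140 − 120 leaves room for only 20 others. The number moved from 100 to 200 mg, and when, is not given, so no share can be computed for them.

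**Labels used elsewhere in the SAP**

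| Place | Dose label |
|---|---|
| SAP 7, planned treatment | Changes at Week 12 and again at titration |
| SAP 7.7, exposure | Split at the switch |
| SAP 7.8.1, second-period AEs | Combination of first- and second-period treatment |
| SAP 7.8.1, further AE analysis | Dose at onset |
| SAP 7.8.2, abnormality counts and Hy's Law figures | Dose at study entry |

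**The case against.** The entry label is not arbitrary. It follows the Treated Set definition in SAP 6.3, keeps each patient in one group and avoids double counting. The trial tests no hypothesis (Protocol 7.2). SAP 6.1 splits laboratory summaries at Week 12, one grade-shift table is by period, and SAP 7 lists all individual values by patient and visit. The liver listing gives the dated course for every patient above 2x ULN bilirubin or 3x ULN ALT or AST, which are the figures' own thresholds. Hepatic-injury events also reach the dose-at-onset AE tables.

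Most of this stands: no data are lost, and every alert point can be traced by date. But a reader must do the tracing. The entire-study summary is planned alongside the split ones, and no split is stated for the figures. The hepatic-injury definition needs ALT or AST at least 3x with bilirubin at least 2x ULN in one sample, or ALT or AST at least 10x ULN. Isolated values above 3x or 2x reach the AE tables only if the investigator judges them clinically relevant (Protocol 5.2.3).

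Two stronger readings are tempting, but the documents do not support them:

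- A reader might infer that the after-Week-12 abnormality table would have none of its 3, 7 or 23 later samples on the labelled dose. That holds only if the entry label also governs that table. SAP 6.1 says subjects are analysed by the treatment they were treated with, SAP 7 redefines planned treatment after Week 12, and 7.8.2 defers to sponsor standards that are not shown. Which label applies is unclear.
- A reader might add placebo and infer up to 120 + 20 = 140 patients. The SAP's AE and efficacy groupings have no placebo column, which suggests that none entered, although SAP 7.7 uses a placebo switcher as its example. Reaching 140 would also leave no room for 100 mg entrants under the open-label ceiling.

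**Conclusion.** The point holds for the entire-study abnormality counts and both Hy's Law figures. For a 25 mg or 50 mg entrant who stays past Week 12, 75.0% of scheduled on-treatment samples to Week 48 and 95.8% to Week 288 are off the labelled dose. Patients moved from 100 to 200 mg have the same problem from titration onwards, and no fixed mapping recovers their dose. This is misattribution in descriptive displays, not loss of data. It should be fixed because the correction is cheap and the displays are meant to show laboratory and liver signals.

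The conclusion assumes that identifying patients by entry treatment means grouping the table that way, which is the natural reading. The counts cover scheduled visits only; Protocol 6.1 allows extra retest visits. The entry label is right for 400 mg patients, 200/200 mg patients, 100/100 mg patients who do not titrate, and anyone who stops before Week 12.

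A separate point concerns the AE sets. SAP 6.1, as it can be read here, lists four but calls dose at onset the fifth, and excludes Part 1 patients stopping before Week 12 from the second and fourth. If the printed order governs, those patients drop out of the dose-at-onset analysis. A lost list item would explain the numbering equally well, so that exclusion should not be taken as intended.

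**What to change.** 1. In the entire-study and after-Week-12 abnormality tables and both Hy's Law figures, replace the entry-dose label with the sequence label of SAP 7.8.1 (for example 25/100 mg). Give patients moved from 100 to 200 mg a separate label or flag.
2. Mark each qualifying or maximum value with the dose taken at the sample, and count a pre-dose sample on a switch day to the previous dose. Do this for ALT (or AST) and bilirubin separately, since the two maxima may fall on different doses.
3. Add current dose to the liver listing.
4. Optionally, add a supportive table by dose at sample, with samples and patient-years shown.
5. Separately, reconcile the set references in SAP 6.1 so that patients stopping before Week 12 are not dropped from the dose-at-onset AE analysis.

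The cost is SAP wording and some table and figure shells. The SAP already uses dosing start and stop dates, sample dates and planned dose after titration.

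The optional table has a downside: patients appear under more than one dose, and sampling opportunity is unequal. Assume a chance p of a qualifying value per sample, independent between samples (in practice they are correlated). The chance of at least one in k samples is 1 − (1 − p)^k. At p = 1% this is 1.0% for the single entry-dose sample, against 3.0%, 6.8% and 20.6% for 3, 7 and 23 later samples. For 23 later samples it ranges from 10.9% (p = 0.5%) to 37.2% (p = 2%). This is why samples and patient-years must be shown.

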7.8.3 Vital signs

Only descriptive statistics are planned for this section of the report.

7.8.4 ECG

Abnormal ECG recordings will be noted, and clinically relevant abnormal findings will be reported as AEs by the investigator.

7.8.5 Others

8. TIMEPOINT OF RELEASE OF TREATMENT INFORMATION

For patients rolled over from Part 1 of trial 1407-0030 the unblinded treatment information will be loaded into the trial database only after all patients have completed the blinded 12-week treatment period.

For patients rolled over from Part 2 of trial 1407-0030 the treatment information will be loaded into the trial database upon entry into study 1407-0005.

11. HISTORY TABLE

Table 11: 1 History table

Version	Date (DD-MMM- YY)	Author	Sections changed	Brief description of change
1	03-MAR-2021	[REDACTED]	None	This is the final TSAP
